### 10.1.2. Serious Adverse Event (SAE)

A serious adverse event (experience) is defined as any adverse experience that suggests a significant hazard, contraindication, side effect, or untoward medical occurrence that:

1. Results in death
2. Is life-threatening
3. Requires or prolongs hospitalization, including emergency room care
4. Causes persistent or significant disability or incapacity
5. Results in congenital anomaly
6. Requires intervention to prevent permanent impairment or damage or in the judgment of the investigator represents significant hazard to the study participant.

### 10.1.3. Assessment of Causality

The relationship or attribution of a medical event or toxicity, or a serious adverse event (being possibly related or not) to an investigational product or therapy represents the best estimate of the principal investigator or sub-investigator at the time of reporting the causal relationship.

The investigator’s determination of treatment-relatedness (attribution) for each medical event or toxicity is recorded in the source documentation. For this protocol, the attribution will be dichotomized into the “possibly related” or “not possibly related” categories.

### 10.1.4. Severity of Adverse Event

AEs will be graded on a scale from 1 to 5 using Collaborative Islet Transplant Consortium *Terminology Criteria for Adverse Events (TCAE) In Trials of Adult Pancreatic Islet Transplantation, Version 5.0 (03 August 2011)*:

Grade 1 = Mild adverse event

Grade 2 = Moderate adverse event

Grade 3 = Severe and undesirable adverse event

Grade 4 = Life-threatening or disabling adverse event

Grade 5 = Death.

Adverse events *not* included in the TCAE listing will be recorded and graded 1 to 5 according to the *General Grade Definitions* provided below (see Table 2).

**Table 2.** General Grade Definitions for Items Not in TCAE Listing

Grade	Descriptor	Definition
1	Mild	Transient or mild discomforts (< 48 hours), no or minimal medical intervention/therapy required, hospitalization not necessary (non-prescription or single-use prescription therapy may be employed to relieve symptoms, e.g., aspirin for simple headache, acetaminophen for post-surgical pain)
2	Moderate	Mild to moderate limitation in activity; some assistance may be needed; no or minimal intervention/therapy required, hospitalization possible
3	Severe	Marked limitation in activity, some assistance usually required; medical intervention/therapy required, hospitalization possible
4	Life-Threatening or Disabling	Extreme limitation in activity, significant assistance required; significant medical/therapy intervention required, hospitalization or hospice care probable
5	Death	Death

#### 10.1.5. Analyses of Adverse Events

Adverse events will be coded to the Medical Dictionary for Regulatory Activities (MedDRA) preferred terms (PT) and system organ classes (SOC) using version 17.0 or higher. All tabular AE summaries will be for treatment-emergent adverse events (TEAE). For all percentages, the number of patients in the ITT population will comprise the denominator.

An overall summary table will be developed to report, across the total safety population and by number of transplants received, starting from the day of first islet cells infusion to the end of 1-year follow-up after the last transplant, the total number of events and the number and percent of patients having at least one event and those related to treatment in the following categories:

a. Procedure Related Events

The incidence and severity of adverse events related to the islet infusion procedure including:

- Bleeding (> 2 g/dl decrease in hemoglobin concentration) identified within 24 hours post transplant.

- Portal vein thrombosis, branch or main, detected by ultrasound by the end of Day 7 (or on the first visit post-transplant if it does not fall on Day 7 exactly).
- Biliary puncture identified within 24 hours post transplant.
- Wound complication (infection or subsequent hernia) identified by the end of Day 7 (or on the first post-transplant visit if it does not fall on Day 7 exactly).
- Increased transaminase levels (> 5 times upper level of normal) identified by the end of Day 30 (or on the post-transplant visit that is closest to Day 30 if it does not fall on Day 30 exactly).

b. Immunosuppression/study drug Related Events

The incidence and severity of adverse events related to immunosuppression and/or the study drug (islets), including:

- Allergy
- Reduction in GFR (> 25% reduction in estimated GFR from baseline by Cockcroft and Gault formula:

$$eC_{Cr} = \frac{(140 - \text{Age}) \times (\text{Weight in kilograms}) \times [0.85 \text{ if Female}]}{72 \times (\text{Serum Creatinine in mg/dL})}$$

- Increase in urinary albumin excretion
- New onset microalbuminuria (albumin > 30 mg/day confirmed by 24 hour urine collection) in patients who were previously within normal limits
- For those patients with baseline microalbuminuria (30-300 mg/day), new onset overt albuminuria (greater than 300 mg/day confirmed by 24 hour urine collection)
- Sensitization evidenced by increase in PRA by at least 20% relative to baseline
- Addition or intensification of antihypertensive therapy
- Oral ulcers
- Lower extremity edema
- Gastrointestinal toxicity (diarrhea)
- Neutropenia (neutrophils < 1.3 thous/ $\mu$ L)
- Anemia (hemoglobin men < 12.1, women < 11.7 g/dL)
- Thrombocytopenia (platelets < 150 thous/ $\mu$ L)
- Infections (viral, bacterial, or fungal)
- Neoplasms, benign or malignant

c. All other TEAEs

The incidence and severity of adverse events reported outside the two aforementioned categories.

The overall summaries will also be done for the following types of AE's:

- SAEs
- TEAEs that lead to discontinuation of the study
- TEAEs resulting in death
- TEAEs graded at least 3 (severe) on the severity scale

In addition to an overall 1-year summary of AEs under each aforementioned category, a summary (number of events and the number and percent of patients having at least one event in the category) by windows of time will be provided for a respective group of AEs after the first transplant: events within the first week (by Day 7), first month (by Day 30), the first three months (by Day 90), the first six months (by Day 180), and the first year (by Day 365). The total number of patients being followed within the specific time window will be used as denominator for calculating the proportion in that time window.

In addition, summaries by SOC and PT will be developed for the following types of AE's:

- TEAEs
- TEAEs reported as related to islet transplantation
- TEAEs reported as having a severe or beyond intensity

The summaries of all TEAEs will present the number of AEs and the number and percent of patients having an AE by SOC and by specific PT. The summary of treatment-related TEAEs and the summary of severe-or-beyond (graded 3-5) AEs will only report the number and percent of patients for each SOC and PT. For the summary of AEs reported as possibly related to islet transplant, missing relationships to the treatment will be counted as possibly related to islet transplant. Likewise, if the maximum severity of an AE is not reported, then the maximum severity of the AE will be imputed.

In addition to these summary tables, patients with treatment-emergent SAEs and patients who discontinued prematurely due to a TEAE will be presented in separate patient listings. The listings will provide all of the information reported for that AE and will include the length of time from study drug administration to the occurrence of the AE. If there are any deaths in the study, a similar listing of all TEAEs for patients who died will be provided.

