#### **4. ANALYSIS POPULATIONS**

**ITT population:** Any patient in whom protocol-directed therapy (e.g., pre-transplant immunosuppression) is initiated will be included in the Intent-to-treat (ITT) population. All efficacy analyses will be on this ITT population regardless whether transplantation occurs or not.

**Safety Population:** Any patient in whom protocol-directed therapy is initiated will be included in the Safety population, which is the same as the ITT population. Patients in this population might not receive an islet transplant. All safety analyses will be on this Safety population.

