## **10. SAFETY EVALUATIONS**

Safety analyses will be conducted for the Safety Population. Summaries will be prepared for the targeted safety endpoints listed below and for all observed adverse events (AE). All patients in the Safety population will be analyzed for safety endpoints for 1 year after the first and the last transplantation (if applicable) or up to the data cut-off date, 13 April 2015.

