#### **10.1.1. Definitions**

The following definitions will be applied consistently to the safety analysis:

Baseline (Clinical Labs, Physical Examinations)	The baseline value will be the result collected at the immediate pre-transplant work-up visit, if scheduled, or the most recent screening visit prior to the islet transplant where the lab/examination was scheduled.
Baseline (Vital Signs)	The baseline value will be the result collected at the immediate pre-transplant work-up visit. If this assessment was not obtained, then the most recent value obtained for

	the specific parameter prior to the islet infusion will be used as the baseline value.
Baseline (ECG parameters)	The baseline value will be the most recent pre-transplant value obtained.
Change from baseline	Value at the time point – value at baseline
Treatment-emergent	Any safety assessment that occurred at the onset of or after start of the first islet infusion, up to the end of 1-year follow-up after the last infusion.

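### Adverse-event tables set 1, 2 and 3 transplants side by side as crude percentages over unequal observation time, and the time-window denominator is not defined

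*SAP*

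**What the plan says.** SAP 10.1.5 plans an overall adverse-event table "across the total safety population and by number of transplants received, starting from the day of first islet cells infusion to the end" of the one-year follow-up after the last transplant. SAP 10.1.1 sets the same window for treatment-emergent events, which count "up to the end of 1-year follow-up after the last infusion". SAP 10 evaluates safety "for 1 year after the first and the last transplantation (if applicable) or up to the data cut-off date, 13 April 2015".

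Shells 14.3.1 and 14.3.3 to 14.3.5 have a Total column and one column each for 1, 2 and 3 transplants, each with its own N. They print numbers and percentages of patients. Event counts are also shown, except in 14.3.5. No patient-time, event rate or censoring-aware estimate is planned for adverse events.

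On denominators, SAP 10.1.5 first states: "For all percentages, the number of patients in the ITT population will comprise the denominator". Later, for the summary by Day 7, 30, 90, 180 and 365 (Table 14.3.2), it states: "The total number of patients being followed within the specific time window will be used as denominator". On who belongs to the ITT and Safety populations, SAP 4 says: "Patients in this population might not receive an islet transplant".

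**The concern.** A patient with one infusion is observed for one year. A patient with three is observed for one year plus two gaps. A patient still ongoing at the cut-off may be observed for less than a year. Crude percentages in adjacent columns mix event risk with length of observation, and a reader can take a difference in follow-up for an effect of repeated transplantation.

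The SAP already recognises the principle: Section 8.2.3 divides severe hypoglycaemic events by days recorded and annualises the HYPO score because the observation period differs between patients. Adverse events get no such treatment.

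Safety is part of the primary objective, and the trial is meant to support a licence application (SAP 2.1). SAP 2.8 contemplates as few as 15 patients; at that size one patient moves a percentage by 1/15 = 6.7 points, so an unclear denominator is not trivial.

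**Working it through.** The documents state no adverse-event rate, so there is no planned figure to reproduce. The size is shown by illustration.

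**1. Gap lengths.** Protocol 6.5.1 makes a subject eligible for another infusion if insulin independence is not met by the end of week 4. It also permits re-transplantation after loss of insulin independence at any time during the 5-year follow-up. Actual gaps are not given, so 28 days, six months and one year are assumed.

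**2. Crude percentage under one common rate.** With constant rate λ and observation T years, the expected proportion with at least one event is 1 − exp(−λT). T is 1 for one transplant, 1 + g for two and 1 + 2g for three, where g is the gap.

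| Assumed rate | Gap | T (years) | 1 / 2 / 3 transplants |
|---|---|---|---|
| 0.5 per year | 28 days | 1, 1.077, 1.153 | 39 / 42 / 44% |
| 0.5 per year | 6 months | 1, 1.5, 2 | 39 / 53 / 63% |
| 10% one-year risk | 28 days | as above | 10.0 / 10.7 / 11.4% |
| 10% one-year risk | 180 days | 1, 1.493, 1.986 | 10.0 / 14.6 / 18.9% |
| 30% one-year risk | 28 days | as above | 30.0 / 31.9 / 33.7% |
| 30% one-year risk | 365 days | 1, 2, 3 | 30.0 / 51.0 / 65.7% |

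Within each row the true rate is the same in every column.

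**3. Ongoing patients.** If 10 of 50 are cut off after half a year (assumed) at 0.5 per year, the crude figure is (40 × 0.393 + 10 × 0.221)/50 = 0.359. So 39% is reported as 36%.

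**4. Procedure-related events.** SAP 10.1.5 ties these to 24 hours, Day 7 or Day 30 after a transplant, so they scale with infusions rather than time. An assumed 10% risk per infusion gives 1 − 0.9^k = 10%, 19% and 27% of patients for k = 1, 2 and 3.

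**5. Denominator of the time-window table.** Assume 50 ITT patients, 2 never infused, a true one-year risk of 30% (λ = −ln 0.7 = 0.357), and a fraction c of the 48 infused leaving or cut off uniformly over year 1. The chance of an event before leaving is 1 − (1 − 0.7)/0.357 = 0.159, so observed events are 48 × [(1 − c) × 0.30 + c × 0.159].

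| c | Events | Over ITT (50) | Over all infused (48) | All events over those followed to Day 365 |
|---|---|---|---|---|
| 10% | 13.7 | 27.4% | 28.6% | 31.8% |
| 20% | 13.0 | 26.1% | 27.2% | 34.0% |
| 40% | 11.7 | 23.4% | 24.4% | 40.6% |

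A fourth reading, with both events and patients restricted to those followed to Day 365, gives 30% throughout if leaving is unrelated to events. Across the readings one cell moves by about 4 points (c = 10%) to 17 points (c = 40%). Because the windows are cumulative, any follow-up within the window includes every infused patient each time, whereas follow-up to its end drops early leavers. The SAP does not say which applies.

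**The case against.** The strongest reply is that these tables are descriptive. SAP 9.2 states that there are no hypotheses beyond the primary analyses, no test by number of transplants is planned, and cumulative burden over a 1-to-3-infusion strategy is a legitimate thing to report. That stands. A reader might infer that the percentages are incorrect; they are not. A crude proportion correctly describes what was observed, and the fourth reading in the check is unbiased if leaving is unrelated to events.

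A reader might also infer that Table 14.3.2 rests on two unreconciled denominators. Shell 14.3.2 prints a separate N under each window, which fits the table-specific sentence. What remains is a wording clash and an undefined term.

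Nor do the documents show that percentages will generally rise with number of transplants. With 28-day gaps the distortion is a few points, small beside the sampling error at n = 50 (1.96 × √(0.39 × 0.61/50) = 13.5 points around 39%). In the Phase 1/2 adverse-event table (Protocol, end of Section 4), anaemia, leukopenia and weight loss each occurred in 10/10 subjects, so such rows would be near 100% in every column. Protocol 6.8.1 withdraws subjects from further transplants after serious, unexpected, related events, which keeps those events in the lower columns and works the other way.

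The SAP also lists infusion dates (14.1.8), disposition (14.1.1) and serious-event onset relative to the latest transplant (14.3.6). These help a careful reader but do not supply a rate.

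**Conclusion.** The point holds as a reporting weakness that should be corrected. Observation time differs by design between the transplant-number columns and is cut short for ongoing patients, and nothing in the adverse-event tables accounts for it. For mid-frequency, time-driven events the artefact runs from a few points with 28-day gaps to more than 20 points with six-month gaps at 0.5 events per patient-year. The constant rate, gaps, risks, never-infused count and leaving fractions are all assumptions.

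On denominators, the intended rule for Table 14.3.2 can be inferred, but its key term needs a definition. Never-infused patients cannot have a treatment-emergent event under SAP 10.1.1, so including them can only dilute the percentages. The Total column of Table 14.3.2 also runs to one year after the last transplant while its neighbours use fixed windows from the first. SAP 10.1.5 calls the overall summary a one-year one, which is not so for anyone re-transplanted.

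**What to change.** - Keep the observed counts and percentages. Add patient-years and events per patient-year to every column of Tables 14.3.1 and 14.3.3 to 14.3.5.
- Report procedure-related events per infusion as well as per patient.
- Use infused patients as the denominator for treatment-emergent events, and exempt Table 14.3.2 explicitly from the ITT sentence. Define what being followed within a window means.
- Add to Table 14.3.2 a cumulative incidence at Days 7, 30, 90, 180 and 365 with 95% confidence intervals. Censor at the cut-off or loss to follow-up, treat death as a competing event, and count an adverse event that leads to withdrawal as an event. A plain Kaplan-Meier estimate that censors deaths and event-driven withdrawals would not be adequate.
- Footnote that number of transplants is a post-baseline grouping and that the columns are descriptive. Patient-years alone do not cure this, since events before a second infusion still fall in the two-transplant column.

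Cost: a few more columns and a little more programming, using dates already collected.

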## **10.2. Concomitant Medications**

All medications used in line with islet transplantation as described in the protocol will be summarized and reported as study concomitant medications. Concomitant medications during the study will include immunosuppressants and other medications that are part of the protocol directed treatment (see Section 2.5, Treatment Regimens) and are reported on the

Current/Prior Medications page of the CRF with a start date/time on or after the date/time when the protocol-directed therapy is initiated.

For the in-study concomitant medications summary, all medications will be coded to preferred drug names and therapeutic drug class using the World Health Organization (WHO) Drug Dictionary Enhanced. Use of concomitant medications across all patients will be summarized for each therapeutic drug class and each preferred drug name.

Patients with treatment-emergent SAEs, patients who discontinued prematurely due to a TEAE and patients who died during the safety evaluation period will be presented in separate patient listings which provide all of the information on prior/concomitant medications administration, include the dosing and schedule of medications, and trough level of immunosuppressants before each dosing change up to the occurrence of the AE/death.

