#### **8.2.4 Analysis of baseline health conditions**

To assess the overall health of the study patients, the following patient characteristics at baseline will be summarized using number and percentage of patients in each category:

- Clinically significant medical histories by body system;
- Clinically significant current medical conditions by body system;
- Abnormal physical examination findings by body system; and
- Prior/Concomitant medication use at baseline.

“Clinically significant” conditions are whichever conditions that by *a priori* decision of the P.I. may affect the outcome of the islet transplant, including autoimmune diseases, pre-existing CVD, any indications of being at-risk for kidney diseases, and pre-existing mild kidney problems. Current medical conditions will include those conditions reported on the Medical History page of the CRF as current up to the date/time of islet transplant. The remaining conditions reported on the Medical History page of the CRF will be counted in the medical history summary. For the medical history summary, the current medical condition summary and the concomitant medication summary, the percent of patients will be based on the total number of patients in the Safety population. For the physical examination summary, the percent of patients will be based on the number of patients for which the specific body system was assessed. This will include all patients for whom the Normal/Abnormal response is not missing or the response is not reported as ‘Not Done’. The results of physical examination throughout the screening phase up to the immediate pre-transplant work-up will be counted accumulatively. However, more than one abnormality identified for a single patient under the same body system will be counted only once.

For the prior/concomitant medication summary, all medications will be coded to preferred drug names and therapeutic drug class using the World Health Organization (WHO) Drug Dictionary Enhanced. Use of prior/concomitant medications will be summarized for each therapeutic drug class and each preferred drug name. Prior/concomitant medications will include medications that are not part of the treatment regimens (see Section 2.5.) reported on the Current/Prior Medications page of the CRF with a start date/time prior to the date/time of initial islet transplant but indicated as ongoing at the last scheduled visit before the first transplant.

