Total # of Tx Received	Subj. No.	Adverse Event System Organ Class/ Preferred Term	Time of Onset (days) [1]	Dur. of AE (days)	Maximum Intensity/ Rel. to Tx	Action Taken/ Outcome	Discon- tinued because of this AE?
1 Tx	XXX	XXXXXXXXXXXXXXXXXXXX/ XXXXXXXXXXXXXXXXXXXX	XX	XXXX	XXXXXXXXXX/ XXXXXXXXXX	XXXXXXXXXX/ XXXXXXXXXX	XXX
	XXX	XXXXXXXXXXXXXXXXXXXX/ XXXXXXXXXXXXXXXXXXXX	XX	XXXX	XXXXXXXXXX/ XXXXXXXXXX	XXXXXXXXXX/ XXXXXXXXXX	XXX
	etc.						
2 Tx's	XXX	XXXXXXXXXXXXXXXXXXXX/ XXXXXXXXXXXXXXXXXXXX	XX	XXXX	XXXXXXXXXX/ XXXXXXXXXX	XXXXXXXXXX/ XXXXXXXXXX	XXX
	XXX	XXXXXXXXXXXXXXXXXXXX/ XXXXXXXXXXXXXXXXXXXX	XX	XXXX	XXXXXXXXXX/ XXXXXXXXXX	XXXXXXXXXX/ XXXXXXXXXX	XXX
	etc.						
3 Tx's	XXX	XXXXXXXXXXXXXXXXXXXX/ XXXXXXXXXXXXXXXXXXXX	XX	XXXX	XXXXXXXXXX/ XXXXXXXXXX	XXXXXXXXXX/ XXXXXXXXXX	XXX
	XXX	XXXXXXXXXXXXXXXXXXXX/ XXXXXXXXXXXXXXXXXXXX	XX	XXXX	XXXXXXXXXX/ XXXXXXXXXX	XXXXXXXXXX/ XXXXXXXXXX	XXX
	etc.						

[1] Relative to the day of the most recent transplant.

XXXXXXXXXX.sas, DMMMMYYY:HHMM

Table 14.3.7  
 Listing of Adverse Events Leading to Premature Discontinuation

Total # of Tx Received	Subj. No.	Adverse Event System Organ Class/ Preferred Term	Time of Onset (days) [1]	Dur. of AE (days)	Maximum Intensity/ Rel. to Tx	Action Taken/ Outcome	SAE?
1 Tx	XXX	XXXXXXXXXXXXXXXXXXXX/ XXXXXXXXXXXXXXXXXXXX	XX	XXXX	XXXXXXXXXX/ XXXXXXXXXX	XXXXXXXXXX/ XXXXXXXXXX	XXX
	XXX	XXXXXXXXXXXXXXXXXXXX/ XXXXXXXXXXXXXXXXXXXX	XX	XXXX	XXXXXXXXXX/ XXXXXXXXXX	XXXXXXXXXX/ XXXXXXXXXX	XXX
	etc.						
2 Tx's	XXX	XXXXXXXXXXXXXXXXXXXX/ XXXXXXXXXXXXXXXXXXXX	XX	XXXX	XXXXXXXXXX/ XXXXXXXXXX	XXXXXXXXXX/ XXXXXXXXXX	XXX
	XXX	XXXXXXXXXXXXXXXXXXXX/ XXXXXXXXXXXXXXXXXXXX	XX	XXXX	XXXXXXXXXX/ XXXXXXXXXX	XXXXXXXXXX/ XXXXXXXXXX	XXX
	etc.						
3 Tx's	XXX	XXXXXXXXXXXXXXXXXXXX/ XXXXXXXXXXXXXXXXXXXX	XX	XXXX	XXXXXXXXXX/ XXXXXXXXXX	XXXXXXXXXX/ XXXXXXXXXX	XXX
	XXX	XXXXXXXXXXXXXXXXXXXX/ XXXXXXXXXXXXXXXXXXXX	XX	XXXX	XXXXXXXXXX/ XXXXXXXXXX	XXXXXXXXXX/ XXXXXXXXXX	XXX
	etc.						

[1] Relative to the day of the most recent transplant.

XXXXXXXXXX.sas, DMMYYYY:HHMM

TABLE 14.3.8  
 Concomitant Medications from Initial Transplant to 1 Year after Last Transplant

Drug Class/ Preferred Drug Name	Islet Transplantation (N=X) n (%)
Subj. taking a con. med.	X (XX)
Drug Class 1	
Preferred Name 1.1	X (XX)
Preferred Name 1.2	X (XX)
Preferred Name 1.3	X (XX)
etc.	
Missing	X (XX)

Note: Medications were coded using WHO Therapeutic drug classes and preferred names.

XXXXXXXXXX.sas, DDMMYYYY:HHMM

Table 14.3.9

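### As defined in SAP 8.2.4 and 10.2, Tables 14.1.7 and 14.3.8 leave non-protocol drugs started after transplant without a by-class or by-drug summary

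*SAP*

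**What the plan says.** Two SAP tables summarise medication by therapeutic class and preferred name.

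- **Table 14.1.7 (baseline), defined in SAP 8.2.4.** On drug type: "Prior/concomitant medications will include medications that are not part of the treatment regimens (see Section 2.5". On dates, the drug must be recorded "with a start date/time prior to the date/time of initial islet transplant but indicated as ongoing at the last scheduled visit" before the first transplant.
- **Table 14.3.8 (on study), defined in SAP 10.2.** The section opens: "All medications used in line with islet transplantation as described in the protocol will be summarized and reported as study concomitant medications". It then states: "Concomitant medications during the study will include immunosuppressants and other medications that are part of the protocol directed treatment", with a reference to Section 2.5. On dates, the drug must be on the "Current/Prior Medications page of the CRF with a start date/time on or after the date/time when the protocol-directed therapy is initiated".

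The title of Table 14.3.8 carries no such limit: "Concomitant Medications from Initial Transplant to 1 Year after Last Transplant".

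Three other places bear on the point. SAP 2.5.3, which lies inside the section that both definitions use as their boundary, ends by allowing further drugs, given under best medical practice, for conditions that arise during the study. SAP 10.1.5 lists "Addition or intensification of antihypertensive therapy" among the targeted safety events. SAP 3.1 requires all data in the clinical database to be listed.

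**The concern.** Both definitions use Section 2.5 as the dividing line, but they take opposite sides of it in different periods. A drug outside the regimens that is started after transplant appears to fall between them.

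This bears on the reading of efficacy. Under SAP 9.1, success needs HbA1c of 6.5% or lower at Day 365 and no severe hypoglycemic event from Day 28 to Day 365. The insulin-independence parameters in SAP 9.2 refer to exogenous insulin, glucose and C-peptide. Neither definition mentions non-insulin glucose-lowering drugs, and protocol exclusion criterion 34 (Section 6.4.2) bars them only within 4 weeks of enrollment. A patient given such a drug after transplant could count as a success, and no planned summary would show it. SAP 2.1 says the trial is to support a license application, and it has a single arm, so no comparator would put co-medication in context.

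It also bears on safety. Drug toxicity that may need treatment is foreseeable. The protocol's Phase 1/2 adverse event table (end of Section 4) reports anemia in 10/10 subjects, neutropenia in 7/10, and LDL and triglyceride elevation in 2/10 each. Protocol 9.1.2 reports raised cholesterol in 15 of the first 17 recipients in the cited series. How many of these were treated is not stated.

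**Working it through.** The plan states no figure on this point, so there is nothing to recompute. The check is a cross-classification of the two definitions, followed by a search of the SAP for any other summary of the same drugs.

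**Step 1. Cross the two rules.**

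| | Started before transplant / therapy initiation | Started after |
|---|---|---|
| Outside the Section 2.5 regimens | Table 14.1.7, if ongoing at the last visit before the first transplant | Neither table, on the plain reading |
| Part of the Section 2.5 regimens | Neither table (not pursued here) | Table 14.3.8 |

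The upper right cell is the gap.

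**Step 2. Test whether the clause in 2.5.3 fills that cell.**

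- *Inclusive reading.* The clause covers only conditions that present during the study. Drugs for such conditions would therefore count as part of Section 2.5 and enter Table 14.3.8, while long-standing treatment of earlier conditions would stay in Table 14.1.7. This reading is coherent.
- *Plain reading.* A drug chosen by the treating physician under best medical practice is not obviously directed by the protocol, so it stays outside Table 14.3.8.
- *What the inclusive reading still omits.* A new glucose-lowering drug given for the diabetes itself treats a condition that was present before the study, so the clause does not reach it.
- *A sign of the ambiguity.* Protocol 6.5.3 has the same clause and gives filgrastim as its example. SAP 2.5 never names filgrastim, so two programmers could classify it differently.

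**Step 3. Look for another planned summary, drug by drug.**

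- Exogenous insulin: its absence at Day 365 is tabulated in Table 14.2.2a.
- Exenatide: a Section 2.5.3 drug, so inside Table 14.3.8.
- Antihypertensives: under SAP 10.1.5, addition or intensification is to be reported as number of events and number and percent of patients, overall and by number of transplants. There is no breakdown by drug, and the Table 14.3.1 shell has no row for this event.
- Other glucose-lowering drugs: no summary found.
- Treatment for anemia or lipids: the anemia event (10.1.5), hematology (Table 14.3.10) and lipid panel (Table 14.3.14) are summarised. The drugs given are not.

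**Step 4. Check the listings.** Table 14.3.9 lists medication in full for patients with an SAE, a discontinuation due to a treatment-emergent event, or death. Listing 16.2.4c is for concomitant medications, and SAP 3.1 requires all database data to be listed. The records are therefore available, but without counts by class or drug.

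**The case against.** The strongest case against the point has four parts.

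- Section 10.2 refers to the whole of Section 2.5, including the open clause in 2.5.3, and the title of Table 14.3.8 is unrestricted. On that view the drugs are already in the table and 10.2 is merely loosely worded. The inclusive reading is indeed possible, and it would not empty Table 14.1.7. It is not the plain reading, however, and it leaves out new treatment for the diabetes itself. What survives of the objection is that the exclusion is not certain.
- The antihypertensive endpoint does not depend on Table 14.3.8. This stands in full. The event is derived from patient-level records, and SAP 10.1.5 plans its count. A reader might infer that the endpoint cannot be evaluated; the documents do not support that.
- Neither document plans non-insulin, non-exenatide glucose-lowering drugs after transplant, so that group may be empty. This is fair, and it is why no size is claimed. An empty group is also a result the tables ought to show.
- Tables of this kind count patients by preferred name and are not designed to show dose changes. This also stands. The absence of dose increases for earlier drugs is a matter of presentation and is not part of this point.

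**Conclusion.** The point holds in a limited form. Read together, SAP 8.2.4 and 10.2 provide no by-class or by-drug summary of non-protocol drugs started after transplant, under a table title that leads the reader to expect one. Section 2.5.3 leaves it unclear whether some of them enter Table 14.3.8.

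A reader might go further and infer that these drugs are reported nowhere. The documents do not support that: they reach the listings, antihypertensive changes have a planned event and patient count, insulin is tabulated at Day 365, and exenatide is inside Table 14.3.8.

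The gap runs from the first transplant to 1 year after the last. The number of drugs or patients affected cannot be derived, because neither document gives rates of treatment for toxicity or of added glucose-lowering drugs. The tables are descriptive, and no primary or secondary estimate changes. What is at stake is whether a reader of the report can see co-medication that bears on HbA1c success and on drug toxicity. The conclusion assumes that the programmers follow the text of 10.2 rather than the table title.

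**What to change.** In SAP 10.2, define on-study concomitant medication as any medication taken from initiation of protocol-directed therapy to 1 year after the last transplant, whatever its start date. Present Table 14.3.8 in two blocks, protocol-directed and other, and identify in the second block the drugs newly started after transplant. State in which block drugs given under the 2.5.3 clause belong, so that cases such as filgrastim are classified in one way only.

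The cost is one revised paragraph, a little more programming and a longer table. SAP 10.2 and 8.2.4 both draw on the Current/Prior Medications page of the CRF, so no new data collection is needed, and no endpoint definition changes.
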